## 1 PROTOCOL SYNOPSIS

Short protocol Title	PanACEA DE lpazolid dose-finding and CO mbination DE velopment (DECODE)								
Full protocol title	A Phase IIb, Open-Label, Randomized Controlled Dose Ranging Multi-Center Trial to Evaluate the Safety, Tolerability, Pharmacokinetics and Exposure-Response Relationship of different doses of Delpazolid in combination with Bedaquiline, Delamanid and Moxifloxacin in Adult Subjects with Newly Diagnosed, Uncomplicated, Smear-Positive, Drug-sensitive Pulmonary Tuberculosis								
Name of IMP	Delpazolid (DZD) 400 mg tablets								
Non-IMP study drugs	Bedaquiline (BDQ), Delamanid (DLM), Moxifloxacin (MXF)								
Indication	Pulmonary Tuberculosis (TB)								
Objectives	Safety and Tolerability Objective:								
	To describe the safety, tolerability and exposure-toxicity relationship of DZD given over 16 weeks, in combination with standard-dose BDQ, DLM and MXF, compared to standard-dose BDQ, DLM and MXF alone								
	Efficacy Objectives:								
	Primary Efficacy Objective :								
	
 
To establish an exposure-response model for DZD, given over 16 weeks in combination with standard-dose BDQ, DLM and MXF, on the change in liquid culture MGIT time to positivity (TTP)
 
								
	Secondary Efficacy Objective:								
	
 
To assess dose and exposure-response relationships for DZD, based on secondary efficacy endpoints, including month-2 culture status in liquid media and on solid media, and time to culture conversion in liquid and on solid media
 
To assess the relative efficacy of increasing DZD doses compared to the background regimen without DZD, based on primary and secondary efficacy endpoints.
 
To assess the proportion of patients who suffer relapse within 12 months post randomization, out of those patients completing 16 weeks of therapy and achieving sustained sputum culture conversion, defined as two successive negative liquid media cultures at or before WK08, with no positives to follow until the week 16 visit.
 
Pharmacokinetics Objectives:
 
								
	Primary Priarmacokinetics Objective:								
	To describe the pharmacokinetics (PK) of DZD through development of a population PK model								

	Secondary Pharmacokinetics Objective:
	• To describe the PK of BDQ, DLM and MXF including their main metabolites
	Mycobacteriology Identification and Characterization Objectives:
	
 
To assess the minimum inhibitory concentrations (MIC) of BDQ, DLM, MXF, DZD of the infecting strain, at baseline and on representative isolate(s) grown at or after WK08.
 

	
 
To investigate the frequency of acquired mutations in the infecting strain over treatment
 

	• In patients with recurrent disease: comparison of initial and recurrence isolate by whole genome sequencing to discriminate relapse from reinfection
Study Design	This will be an open label Phase IIb dose-finding, randomized, controlled study with a duration of 16 weeks of experimental therapy of DZD – Bedaquiline/Delamanid/ Moxifloxacin (BDM) in adult patients with newly diagnosed, smear positive, uncomplicated, drug sensitive pulmonary tuberculosis (TB) to evaluate the safety, efficacy, tolerability, pharmacokinetics and exposure/response-relationship of different doses of delpazolid in combination with bedaquiline, delamanid and moxifloxacin.
	Participants will be randomized to one of five arms containing BDM with different doses of DZD:
	
 
Arm 1 (D0): 15 patients will receive 0 mg of DZD
 
Arm 2 (D400): 15 patients will receive 400 mg DZD orally once daily
 
Arm 3 (D800-OD): 15 patients will receive 800 mg DZD orally once daily
 
Arm 4 (D1200): 15 patients will receive 1200 mg DZD orally once daily
 
Arm 5 (D800-BD): 15 patients will receive 800 mg DZD orally twice daily
 

Decision rule for managing post week 16 treatment or follow - up	Patients will stop therapy after the week 16 visit, if they achieve early sputum culture conversion (SCC) to negative. This is defined as two successive negative liquid media cultures, the first of which is at or before week 08, with no positive cultures to follow.
	Results for the negative cultures need to be available by the week 16 (day 112) visit, with a time window of +6 days to accommodate for late availability of culture results, in order for patients to stop therapy.
	Post treatment follow-up visits at weeks 18, 26, 38 and 52 will serve to determine whether they have achieved lasting cure. Patients with a positive culture or other indication as described under 11.4 during the follow up period will undergo a standardized assessment for potential poor treatment outcome. If this procedure results in a diagnosis of recurrent disease, they will be referred to the national TB program.
	Patients who do not achieve SCC as defined above will be referred to the national TB program for standard of care TB treatment according to national guidelines, to complete at least 6 months of treatment in total.
	In addition to the rule above, additional positive sputum LAM testing results late in treatment may be used to enhance detection of patients at risk for unfavourable outcome,

	who would NOT qualify for treatment stop after 16 weeks. The sponsor will produce a centralized decision rule when kits for this assessment become available.								
Time Schedule	Per Subject: 52 weeks in total, including a 36-week follow-up Study duration: Anticipated Recruitment Period: Q3 2021 – Q1 2022. Study duration: Planned End Date (LPLV): Q2 - Q3 2022								
Population	A total of 75 male or female subjects, aged between 18 and 65 years with newly diagnosed, drug sensitive, uncomplicated, smear-positive, pulmonary TB will be included								
Sample size	To be analysed: N = 15 patients per arm with a total of N = 75 patients, and a wide range of DZD doses (from 0mg to 800mg BID) has been determined as an adequate sample size for population PK modelling, and for exposure-response modelling to detect a clinically meaningful dose-dependent relationship.								
Dosage and Administration	Bedaquiline: will be dosed as per the licensed dose: 400 mg orally once daily for the first 14 days, then 200 mg orally three times a week.								
	Delamanid: will be dosed as per the licensed dose: 100 mg orally twice daily (totalling 200mg daily)								
	Moxifloxacin: will be dosed as per the licensed dose: 400 mg orally once daily								
	Delpazolid: not licensed: Current experience in humans up to Phase 2a. Dose according t randomization to dosing arm:								
	
 
Arm 1 (D0): 15 patients will receive 0 mg of DZD
 
Arm 2 (D400): 15 patients will receive 400 mg DZD orally once daily
 
Arm 3 (D800-OD): 15 patients will receive 800 mg DZD orally once daily
 
Arm 4 (D1200): 15 patients will receive 1200 mg DZD orally once daily
 
Arm 5 (D800-BD): 15 patients will receive 800 mg DZD orally twice daily
 
								
	All above drugs will be given for 16 weeks.								
Evaluation Criteria	Primary Endpoints								
	The safety of DZD will be assessed by evaluation of AEs during treatment and follow-up phase, including assessments of vital signs, physical examinations, weight, detailed neurological examinations, colour vision and visual acuity tests, 12-lead ECG, and routine clinical laboratory tests (including chemistry, haematology and urinalysis data).								
	Primary Safety Endpoint								
	
 
Proportion of patients experiencing expected oxazolidinone class toxicities, including peripheral or optical neuropathy, incident leukopenia, anemia or thrombocytopenia, or adverse events in line with tyramine pressor response, of Grade 2 or higher, possibly, probably or definitely related to DZD
 
								
	Primary Efficacy Endpoint								

The efficacy of DZD will be evaluated by measuring the change in mycobacterial load over									
time on treatment as quantified by time to positivity in BD MGIT 960 ® liquid culture									
described by non-linear mixed-effects methodology									
Secondary Endpoints									
Secondary safety endpoints									
All adverse events									
Adverse events of Grade 3 severity or higher									
Adverse events possibly, probably or definitely related to study drugs									
• Treatment discontinuations or interruptions related to adverse events/serious adverse events									

 
Frequency, severity and type of ECG alterations
 
									

 
Changes in ECG intervals of PR, RR, QRS, QT, Fridericia-corrected QT [QTcF]
 
									

 
Proportion of participants with QTcF > 500ms in ECGs on treatment
 
									
• Proportion of participants with a prolongation of QTcF of grade 3 and above as defined under 14.6.									
Secondary Efficacy Endpoints:									

 
Proportion of patients who suffer relapse, defined as recurrent disease caused by a strain identical to the baseline isolate, within 12 months post randomisation, out of patients completing 16 weeks of therapy and achieving stable culture conversion to negative (SCC) as defined below by week 08, with no positives to follow by the week 16 visit.
 
									

 
Time to recurrent TB, and to relapse, within 12 months post randomisation
 
Time to stable sputum culture conversion (SCC) to negative on liquid media (defined as two negative cultures without an intervening positive culture). Time will be measured as time on treatment until the first negative culture.
 
									

 
Proportion of participants who achieved SCC at each time point during treatment
 
Proportion of participants with negative sputum culture on solid media at WK 08 and other timepoints.
 
									

 
Proportion of participants developing drug resistance among those not converting to negative culture
 
									
Pharmacokinetic Endpoints									
A population PK model will be developed for DZD. The following secondary parameters will be derived for DZD, for BDQ, DLM and their main metabolites, and for MXF:									

 
Area under the plasma concentration curve from morning dosing to 24 hours (AUC 0-24) on day 14 (WK2)
 
									
• The observed maximum concentration (C max ) on day 14									
• Time to reach C max (T max ) on day 14									
• The minimum observed plasma concentration (C min ) at day 14 (24 hours following the last dose for intake once daily (QD) and 12 hours following the last dose for twice daily intake (BID))									
Apparent oral clearance (Cl/F)									

	Apparent volume of distribution (Vd/F)							
	• Terminal half-life (t 1/2 )							
	Mycobacteriology Identification and Characterization Endpoints							
	Sputum cultures grown from various timepoints will be assessed as follows:							
	
 
Minimum inhibitory concentrations (MIC) of BDQ, DLM, MXF, DZD, from a baseline isolate, and a representative isolate obtained at or after WK08, if any.
 
Frequency of acquired mutations in the infecting strain over treatment assessed by whole genome sequencing
 
Comparison between bacterial strain causing recurrent disease, and the strain at baseline by whole genome sequencing, to discriminate relapse from re-infection
 
							
	Exploratory endpoints							
	Exploratory endpoints will be analysed depending on laboratory capacity, availability of test kits and budget, and may not be tested in all trial sites equally.							
	
 
Rate of change in molecular bacterial load assay (MBLA) during treatment
 
Time to stable culture conversion to negative in MBLA (defined as two negative MBLAs without an intervening positive)
 
Rate of change in bacterial load measured by quantification of sputum lipoarabinomannan (LAM) during treatment
 
							
Analysis timepoints	Analysis for the primary endpoints, and secondary endpoints unrelated to disease recurrence or relapse, will be performed after data are available (allowing for time for culture growth) after the last patient completed their WK16 (or otherwise last treatment) visit. A partial database lock will be performed for this purpose, with a final database lock at the end of study after all long-term outcome data are available.							
Safety data review trigger rules	An independent data safety monitoring board (DSMB) will be convened for the trial. The DSMB will review safety data at regular intervals, but will also perform expedited review if the following conditions are met:							
	
 
Four or more patients experience a grade 3 or higher AE (CTCAE version 5.0) in the same organ system that are at least possibly related to one of the study drugs, and qualify as "unexpected" by being more severe than in previous experience with the drug in question.
 
							
	• Two or more patients experience a grade 4 or higher AE (CTCAE 5.0) in the same organ system that are at least possibly related to one of the study drugs, and qualify as "unexpected" by being more severe than in previous experience with the drug in question							
	
 
One patient experiences a grade 5 AE (death) that is at least possibly related to one of the study drugs
 
							

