Protocol No: PanACEA - DECODE – 01/ LCB01-0371-20-2-02 Protocol Version No: V2.1, dated 08 September 2021

- A) Continuation Treatment and follow-up visits: Participants of all 5 arms will complete their experimental treatment on Day 112. Omission of anti-TB treatment after this and conduct of follow-up visits 2-3 will be conditional on culture conversion with first negative at or before WK08 (see decision rule). Participants who do not convert to negative culture will receive standard TB treatment according to their national TB program through governmental clinics, and will not have visits FU 2 and FU3. FU 4 will be conducted for all participants.
- B) Serum pregnancy test: blood samples of 7.5mL; for women of childbearing potential only.
- C) HIV Testing: blood samples of 7.5mL will be taken; CD4 count if HIV positive. If the patient is on ARVs at the time of screening, perform viral load count. Genotypic resistance testing mandatory if viral load is insufficiently controlled (>1,000 copies/μl) and patient would need to be switched back to a non-dolutegravir regimen after the study, recommended otherwise.
- D) Urine drug screening: for opiates, amphetamines, cannabinoids, cocaine, benzodiazepines and barbiturates. Results on other drugs generated by a combination test may be used as well.
- E) Sputum sampling: 3 sputa will be collected per time point during treatment phase, 1 spot sputum at SCR and 2 at FU 1-4 each. Two spot sputum samples during treatment and follow-up phase will be processed for mycobacterial culture MGIT liquid culture at all time-points. LJ will be performed at WK00, WK08, WK12, WK16, and FU1-FU4 from two samples each. An isolate from baseline, and all isolates from all cultures positive after WK08 will be stored. The third sputum sample may be a spot or an early morning sputum, and will be stored for future biomarkers work. A Ziehl-Neelsen stained sputum smear will be performed at SCR and WK16 from concentrated sputum and at additional visits as required by the national TB programs.
- F) Physical examination and vital signs: Additional Blood pressure and heart rate recordings WK00 at 1h, 2h and 3h (± 10 mins) after intake of IMP and WK02 during hospitalization at 1h, 2h, 3h, 4h, 6h (± 10 mins) after intake of IMP with a meal. During follow up visits FU 2-4 symptom orientated physical examination only or to follow up on (S)AEs.

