# 13.9 Safety: expedited safety data review

An independent data safety monitoring board (DSMB) will be convened for the trial. The DSMB will review safety data at regular intervals as defined in the DSMB Charter, but will also perform expedited review if the following conditions are met:

- Three or more patients experience a grade 3 or higher AE (CTCAE 5.0) in the same organ system that are at least possibly related to one of the study drugs, and qualify as "unexpected" by being more severe than in previous experience with the drug in question.
- Two or more patients experience a grade 4 or higher AE (CTCAE 5.0) in the same organ system that are at least possibly related to one of the study drugs, and qualify as "unexpected" by being more severe than in previous experience with the drug in question.
- One patient experiences a grade 5 AE (death) that is at least possibly related to one of the study drugs

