#### 18.1.2 Data Safety Management Board (DSMB)

To include an element of expert advice that is independent of the PIs and the sponsor, an independent Data Safety Monitoring Board (DSMB) will be installed. The DSMB will safeguard the interests of trial participants. The DSMB will review data and will make recommendations to the TSC regarding stopping of certain arms, or the whole trial if trial participation is an undue risk to participants and will use the safety review guidelines in their consideration. The DSMB are not executive, any decision regarding early termination of arms or the whole trial will be made by the TSC and sponsor. A DSMB charter will be established that describes the roles and responsibilities of this independent committee for the trial.

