Version	Date	Reason for change	Protocol version	Dates of relevant trial activities (interim and final analyses)	
1.0	13/Feb/2023		Version 2.1, 8/Sep/2021	First version.	

2. Introduction

This Statistical Analysis Plan (SAP) describes the statistical methods to be used during the analysis and reporting of baseline, efficacy safety and pharmacokinetic (PK) data collected for Protocol PanACEA - DECODE - 01. This SAP applies to the output produced for inclusion in the Clinical Study Report (CSR). All outputs required by ICH E9 statistical principles for clinical trials ¹ will be produced.

This SAP should be read in conjunction with the Study Protocol, Case Report Forms (CRF), and Data Management Plan (DMP).

3. Objectives of the Study

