4.4. Early Stopping Rules

An independent data safety monitoring board (DSMB) will be convened for the trial. The DSMB will review safety data at regular intervals as defined in the DSMB Charter, but will also perform expedited review if the following conditions are met:

- Three or more participants experience a grade 3 or higher AE (CTCAE 5.0) in the same organ system that are at least possibly
 related to one of the study drugs, and qualify as "unexpected" by being more severe than in previous experience with the drug
 in question.
- Two or more participants experience a grade 4 or higher AE (CTCAE 5.0) in the same organ system that are at least possibly
 related to one of the study drugs, and qualify as "unexpected" by being more severe than in previous experience with the drug
 in question.
- One patient experiences a grade 5 AE (death) that is at least possibly related to one of the study drugs.

Refer to DECODE Protocol and DSMB charter for more individual patient safety stopping criteria.

5. Trial Endpoints

5.1. Primary Endpoint:

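### The synopsis calls expedited DSMB review at four patients with a qualifying grade 3+ adverse event; Protocol 13.9 and SAP 4.4 call it at three

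*Protocol*

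**What the plan says.** Three places state when the DSMB must hold an expedited review in addition to its regular ones.

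- **Protocol synopsis, row on safety data review triggers:** "Four or more patients experience a grade 3 or higher AE (CTCAE version 5.0) in the same organ system".
- **Protocol 13.9:** "Three or more patients experience a grade 3 or higher AE (CTCAE 5.0) in the same organ system".
- **SAP 4.4:** "Three or more participants experience a grade 3 or higher AE (CTCAE 5.0) in the same organ system".

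In each place the events must also be at least possibly related to one of the study drugs, and unexpected in the sense of being more severe than earlier experience with that drug. The action is the same in each: expedited DSMB review.

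The other two triggers do not differ. For grade 4, Protocol 13.9 reads "Two or more patients experience a grade 4 or higher AE (CTCAE 5.0) in the same organ system", and the synopsis and SAP 4.4 also say two. One related death is enough in all three places.

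Both counts are in force. The protocol's page header reads "Protocol Version No: V2.1, dated 08 September 2021", and the synopsis and 13.9 belong to that one document. The SAP's Document History names the protocol version it was written against as "Version 2.1, 8/Sep/2021".

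**The concern.** A safety trigger should have one value. When the third qualifying patient appears, a reader of 13.9 or the SAP must call an expedited review, and a reader working from the synopsis need not. The qualifiers and the action match, so these are not two rules for two kinds of event. The grade 4 and grade 5 triggers agree everywhere, which leaves the grade 3 count as the only discrepancy.

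Prior exposure is short. Protocol 6.1.4 puts the longest human dosing of delpazolid at 21 days, whereas this trial doses for 16 weeks. Section 5 says that the class toxicities tend to appear later in treatment. Protocol 18.1.2 adds that the DSMB, in advising on stopping arms or the trial, "will use the safety review guidelines in their consideration". If those guidelines are or include these triggers, which the text does not spell out, the DSMB has been given two versions of one of them.

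**Working it through.** **Side-by-side comparison.** The thresholds are stated, not derived, so the plan has no figure to reproduce.

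| Trigger | Synopsis | Protocol 13.9 | SAP 4.4 |
|---|---|---|---|
| Grade 3+, same organ system | 4 | 3 | 3 |
| Grade 4+, same organ system | 2 | 2 | 2 |
| Grade 5 | 1 | 1 | 1 |

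Protocol 13.9 refers to the DSMB Charter only for the regular review intervals. SAP 4.4 does the same and also points to the protocol and Charter for individual patient stopping criteria. Neither says which grade 3+ count prevails.

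**How often the difference could matter.** Inputs:

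- N = 75 (Protocol 10.2). All patients count, because the rule covers any study drug and every arm receives study drugs.
- p, the chance that a patient has a qualifying event in a given organ system. The documents give no value. Protocol 6.1.4 reports no deaths or SAEs in the three oral dose-escalation studies, but dosing there lasted at most 21 days. I therefore assume a range of 1% to 10%.
- Patients are taken as independent, and one organ system is considered.

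With X ~ Binomial(75, p), the review is reached with probability P(X ≥ 3) under 13.9 and the SAP, and P(X ≥ 4) under the synopsis. The gap is P(X = 3) = C(75,3) p³ (1 − p)⁷².

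| Assumed p | P(X ≥ 3) | P(X ≥ 4) | Gap, P(X = 3) |
|---|---|---|---|
| 1% | 0.040 | 0.007 | 0.033 |
| 2% | 0.190 | 0.064 | 0.126 |
| 3% | 0.392 | 0.188 | 0.203 |
| 4% | 0.581 | 0.353 | 0.229 |
| 5% | 0.730 | 0.520 | 0.210 |
| 8% | 0.945 | 0.860 | 0.085 |
| 10% | 0.984 | 0.950 | 0.034 |

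The gap is largest at p = 3/75 = 4%.

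**Allowing for the grade 4 trigger.** Two grade 4+ cases call the review under every text. If a share f of qualifying cases is grade 4+ (assumed), the texts still differ at three cases only when at most one of the three is grade 4+. That has probability (1 − f)³ + 3f(1 − f)²:

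- f = 10%: 0.972, so the largest gap becomes 0.972 × 0.229 = 0.22
- f = 20%: 0.896, giving 0.20
- f = 30%: 0.784, giving 0.18

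The grade 5 trigger is not modelled and would reduce these further.

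**What the gap leaves out.** It measures reviews never called under the synopsis because the trial ends at three cases. If a fourth case follows, the synopsis count delays the review from the third case to the fourth, and the gap does not include that delay. Apart from the grade 4 and 5 triggers, P(X ≥ 3) is the chance that the texts disagree at some moment: 0.58 at a 4% rate and 0.98 at 10%.

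**The case against.** Nobody disputes the mismatch. The case against giving it weight has five parts.

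*The consequence is small.* This stands. The count does not stop anything, and Protocol 18.1.2 says of the board: "The DSMB are not executive". Regular DSMB review, SAE reporting within 24 hours (14.9), the 24-hour reporting of non-serious grade 4 events judged probably or definitely related (14.3) and the individual stopping criteria (13.10) all apply under either count. No endpoint, sample size or analysis uses it.

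*The texts can be obeyed together.* Reviewing at three satisfies all of them, since the synopsis does not forbid an earlier review. That is true, but it helps only someone who has read 13.9 or the SAP. Someone who relies on the synopsis has no prompt to act at three.

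*The probabilities are assumed, and cover one organ system.* This also stands. They show a range and are not a forecast for the trial. The finding rests on the comparison of texts and not on them. Leaving out delayed reviews understates the effect.

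*The link to advice on stopping arms is inferred.* Section 18.1.2 does not identify its guidelines as these triggers, and they could be in the Charter. The link is therefore a supporting reason only.

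*A protocol change is more than one word of effort.* Section 18.7 requires an amendment for any protocol change. This bears on the cost and not on whether the texts conflict.

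**Conclusion.** The concern holds: the synopsis contradicts Protocol 13.9 and SAP 4.4 by one patient on a safety trigger, in current text, and nothing in the two documents settles it. Three is the likely intended number, because the operative section and the SAP both give it. That is not proven: SAP 4.4 repeats 13.9 almost word for word, so it is weak independent evidence, and the DSMB Charter, which may already fix the count, was not available.

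The practical effect is one expedited review, missed or delayed. Under the assumed 1% to 10% rates, a missed review has a probability of 3% to 23% for one organ system, or at most 18% to 22% once the grade 4 trigger is allowed for. It should be corrected, but it does not threaten the trial's conclusions.

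**What to change.** In the synopsis row on safety data review triggers, change the grade 3+ count from four to three, so that it matches Protocol 13.9 and SAP 4.4 and takes the more protective value. Confirm that the DSMB Charter also says three.

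The edit is one word, and design, sample size and analysis are unchanged. Under Protocol 18.7 it has to be made by amendment: a change affecting participant safety goes to the ethics committees and regulators before it takes effect, and a minor administrative one is submitted for notification. It could be carried in the next amendment, with the DSMB told in the meantime that three applies. If three turns out not to have been intended, the cost is at most an expedited review held one case early.
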